- Other applicable regional and local regulations
- Clinical trial contractual obligations

CLINICAL TRIAL TITLE:

enliGHten: A Multicenter, Phase 3, Long-term, Open-label Trial Investigating Safety and Efficacy of TransCon hGH Administered Once-Weekly in Children with Growth Hormone Deficiency (GHD) Who Have Completed a Prior TransCon hGH Clinical Trial

PPD
PPD MD PPD
Date
Ascendis Pharma Inc.

SUMMARY OF CHANGES – VERSION 2.0 (GLOBAL AMENDMENT 1), JANUARY 2020

RATIONALE

This amendment serves to clarify that investigator judgement is the foundation of reporting adverse events (AEs) associated with out-of-range laboratory values. It is recognized that IGF-1 and IGFBP3 are pharmacodynamic markers for TransCon hGH therapy and may be used to guide an investigator’s recommendation to titrate the study drug dose. In prior versions of this protocol, investigators were compelled to label out-of-range IGF-1 and IGFBP3 values as “clinically significant” (regardless of presence of clinical concern, signs, or symptoms) in order to pursue dose titrations. Additionally, clinically significant laboratory values (including IGF-1 and IGFBP3) were categorically to be documented as AEs. This amendment revises the protocol language so that TransCon hGH dose titrations may occur with or without the labeling of out-of-range IGF-1 and/or IGFBP3 as “clinically significant.” It also specifies that out-of-range laboratory values may constitute AEs if they induce a new/worsening diagnosis, clinical sign, or symptom, or require therapy.

Section(s)	Change	Rationale
Protocol version	Global Amendment 1.0 supersedes U.S. (country-specific) Amendment 1.0.	U.S. had a country-specific amendment (US Specific Amendment 1.0) to include protocol changes only designated in the U.S. for the GH Auto-Injector and Dual Chamber Cartridge (DCC) system. This Version 2.0 (Global Amendment 1) applies to all regions, unless otherwise specified. Thus, U.S. will continue from U.S. Amendment 1.0 to Version 2.0 (Global Amendment 1) while all other countries will move from original protocol to Version 2.0 (Global Amendment 1).Country-specific amendments will be applied, as needed, to this version and will be identified as Version 2.1 in that country.

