Note: Any subjects with a history of scoliosis should be monitored for progression of scoliosis.
- Pancreatitis - Cases of pancreatitis have been reported rarely in children and adults receiving hGH treatment, with some evidence supporting a greater risk in children compared with adults. Pancreatitis should be considered in any hGH-treated subject, especially a child, who develops persistent severe abdominal pain.

AEs may include:

- Clinically significant treatment-emergent physical examination abnormalities
- Out-of-range lab or test results associated with new/worsening diagnosis, clinical sign, or symptom; or that require therapy

In this trial, all AEs that are considered mild and not related to investigational product will not be recorded on the AE CRF; this is with the exception of site-specific reporting preferences. In addition, the following out-of-range laboratory values—whether or not associated with a titration of the TransCon hGH dose—will not be considered AEs unless they are associated with a sign or symptom: IGF-1, IGF-1 SDS, IGFBP3, IGFBP3 SDS. In this trial, IGF-1 and IGFBP3 are pharmacodynamic markers of TransCon hGH therapy and may be used to guide an investigator's recommendation to titrate the TransCon hGH dose.

The Medical Expert will review all safety information on an ongoing basis. The key safety data will also be reviewed periodically by an ISC in accordance with its governing charter.

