12.1.3. Reporting Procedures for All Adverse Events

At each visit, all AEs will be documented in response to a general question about the subject's well-being and whether any possible changes in well-being have occurred since the previous visit. Additionally, at each visit, site staff will review subject diary data with the subject and parent/legal guardian/caregiver, to determine if diary entries reflect any AEs. There will be no direct questioning to solicit possible AEs. AEs reported up to 14 days after the final dose of TransCon hGH will be captured. AEs, including SAEs, will be documented through the end of the subject's participation in the trial. All AEs ongoing at the completion of the study or Early Termination Visit must be followed until the event is resolved or deemed stable by the investigator. In this trial, all AEs that are considered mild and not related to investigational product will not be reported on the AE CRF. In addition, the following out-of-range laboratory values—whether or not associated with a titration of the TransCon hGH dose—will not be considered AEs unless they are associated with a clinical sign or symptom: IGF-1, IGF-1 SDS, IGFBP3, IGFBP3. In this trial, IGF-1 and IGFBP3 are pharmacodynamic markers of TransCon hGH therapy and may be used to guide an investigator's recommendation to titrate the TransCon hGH dose. Reportable AEs must be recorded on the appropriate eCRF. Reportable AEs either observed by the investigator or reported by the subject must be recorded regardless of causality.

The following attributes must be documented for each reported AE:

- Subject ID
- Description

- Onset date (if AE was present on Day 1, include whether onset was prior to or after first dose of investigational product)
- Resolution date, if applicable
- Severity
- Causality (relationship to investigational product)
- Outcome
- Action taken
- Determination of “serious” (or not)

Any ongoing AEs from the prior trial will be followed until resolution or stabilization. Any changes to the conditions documented as medical history during the trial and that meet the above AE definition should be recorded as AEs so that a complete safety profile of the investigational product is obtained. See Section 12.2.2 for additional reporting procedures for serious AEs.

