Any change from baseline health status that meets the above AE definition and occurs from the time of the first administration of investigational product until the completion of the study or the Early Termination Visit will be recorded as an AE.

Out-of-range laboratory values or test results may constitute AEs if they:

- induce a new/worsening diagnosis, clinical sign, or symptom, or
- require therapy.

Routine titration of chronic, concomitant medications (eg, increase of levothyroxine dose due to interval weight gain and without associated signs/symptoms of overt hypothyroidism) would not be considered as AEs. Whenever possible, an AE should be recorded as a specific diagnosis or syndrome rather than as a sign, symptom, or out-of-range laboratory value. If there is not a diagnosis, the event term should be the clinical sign or symptom. Based on an investigator’s clinical judgement, multiple concurrent symptoms should be grouped together as a single, unifying diagnosis (e.g. headache, fever, cough, and coryza constitute a probable viral upper respiratory tract infection, and this single AE term is more appropriate than listing each symptom as a separate AE).

Care should also be taken to record the most medically appropriate term (eg, hypertension for elevated blood pressure that persists and requires chronic treatment and follow-up, or increased blood pressure for elevated blood pressure that occurs for a limited time and does not persist or require ongoing treatment).

AEs will be documented at the maximum intensity experienced. If a previously recorded AE or condition recorded as part of medical history increases in severity or frequency, it will be recorded as a new AE.

All AEs will be considered ongoing until they have completely resolved or, in the case of a condition recorded as part of medical history, returned to baseline status prior to investigational product administration. At study completion or the Early Termination Visit, all AEs should have a statement regarding resolution.

Any SAE that is determined to be related to the investigational product will be followed until resolution or stabilization.

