8.7. OTHER ASSESSMENTS.....	22

9.	EFFICACY ANALYSES	22
9.1.	ANNUALIZED HV	22
9.2.	Δ HSDS	22
9.3.	IGF-1 SDS AND IGFBP-3 SDS	23
9.4.	SUBGROUP ANALYSIS.....	23
10.	PHARMACODYNAMICS ANALYSES	24
11.	PATIENT-REPORTED OUTCOMES.....	24
11.1.	PREFERENCE QUESTIONNAIRE.....	24
11.2.	CHILD SHEEHAN DISABILITY SCALE	24
11.3.	CONVENIENCE & OVERALL SATISFACTION DOMAINS OF THE TREATMENT SATISFACTION QUESTIONNAIRE FOR MEDICATION.....	25
11.4.	DEVICE USABILITY QUESTIONNAIRE.....	25
12.	REFERENCES.....	26

List of Abbreviations

ΔHSDS	change in height standard deviation score
μg	microgram
ADHD	attention-deficit/hyperactivity disorder
AE	adverse event
AGHD	adult growth hormone deficiency
C&OS-C	Convenience & Overall Satisfaction domains of the abbreviated 9-item Treatment Satisfaction Questionnaire for Medication - Child
C&OS-P	Convenience & Overall Satisfaction domains of the abbreviated 9- item Treatment Satisfaction Questionnaire for Medication - Parent
cm	centimeter
CSDS-C	Child Sheehan Disability Scale – Child
CSDS-P	Child Sheehan Disability Scale – Parent
eCRF	electronic case report form
FDA	Food and Drug Administration
GCP	Good Clinical Practice
GH	growth hormone
GHD	growth hormone deficiency
HbA1c	hemoglobin A1c
HV	height velocity
ICH	International Council on Harmonization
ICF	informed consent form
IEC	Independent Ethics Committee
IGF-1	insulin-like growth factor-1
IGFBP-3	insulin-like growth factor binding protein-3
kg	kilogram
MedDRA	Medical Dictionary for Regulatory Activities
mg	milligram
mL	milliliter
mPEG	methoxypolyethylene glycol
PD	pharmacodynamics
PQ-C	Preference Questionnaire – Child
PQ-P	Preference Questionnaire – Parent
SAE	serious adverse event
SAP	statistical analysis plan
SD	standard deviation
SDS	standard deviation score
TQSM	Treatment Satisfaction Questionnaire for Medication
TSQM-9	Abbreviated 9-item Treatment Satisfaction Questionnaire for Medication
WHO	World Health Organization

1. Overview

This Statistical Analysis Plan (SAP) describes and supplements the planned analysis and reporting for Ascendis Pharma Endocrinology Division A/S protocol TransCon hGH CT-301 EXT (enliGHten: A Multicenter, Phase 3, Long-term, Open-label Trial Investigating Safety and Efficacy of TransCon hGH Administered Once-Weekly in Children with Growth Hormone Deficiency (GHD) Who Have Completed a Prior TransCon hGH Clinical Trial), Protocol 1.0 dated 29 August 2017.

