8.1. Adverse Events

AE is defined as any untoward medical occurrence in a clinical investigation subject administered a pharmaceutical product and which does not necessarily have a causal relationship with the treatment. An AE can therefore be any unfavorable and unintended sign (including

abnormal laboratory finding), symptom, or disease temporally associated with the use of a medicinal (investigational) product, whether or not related to that product. An AE can arise with any use (e.g., in combination with another drug), route of administration, formulation, or dose, including an overdose.

An AE is considered treatment emergent, i.e., Treatment Emergent Adverse Event (TEAE), is any AE that was first occurred or worsened after the first dose in this extension study and before the end of study. If the AE has any missing start date, the rules stated in Section 5.2 will be applied to determine if it is treatment-emergent.

A serious AE (SAE) is SAE is any untoward medical occurrence that:

- Results in death
- Is life-threatening
- Requires inpatient hospitalization or prolongation of an existing hospitalization
- Results in persistent or significant disability/incapacity
- Is a congenital anomaly/birth defect

Summaries of incidence rates (frequencies and percentages) of individual TEAEs by MedDRA SOC and preferred term will be prepared. Such summaries will be displayed for all TEAEs, TEAEs by maximum intensity, and TEAEs by strongest relationship to study drug. In addition, related TEAE, non-related TEAE, TEAE leading to study drug discontinuation, and serious TEAE, by SOC, the preferred term and TEAE by preferred term will be also summarized. Especially, related includes definite, probable and possible relationship. Not-related includes unlikely/remote and unrelated/not related.

Each subject will be counted only once within each preferred term. If a subject experience more than one TEAE within a preferred term, only the TEAE with the strongest relationship or the maximum intensity, as appropriate, will be included in the summaries of relationship and intensity.

Data listing of AEs, TEAE leading to study drug discontinuation, serious TEAE will also be provided.

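### SAP 8.1 keeps the Protocol 1.0 adverse-event definition and pools TEAEs recorded under a broader and then a narrower laboratory rule, with no sensitivity analysis

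*SAP*

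**What the plan says.** SAP 8.1 defines the AE that feeds the TEAE tables. The wording is "An AE can therefore be any unfavorable and unintended sign (including", continuing "abnormal laboratory finding), symptom, or disease temporally associated with the use of a medicinal (investigational) product". No condition is attached to the laboratory finding. SAP section 1 names the protocol it serves as "Protocol 1.0 dated 29 August 2017".

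The current protocol is Version 2.0. Section 12.1.1 gives, as something an AE may include, "Out-of-range lab or test results associated with new/worsening diagnosis, clinical sign, or symptom; or that require therapy". Section 12.1.3 repeats the condition, opening with "Out-of-range laboratory values or test results may constitute AEs if they". For the growth-factor markers, section 12.1.3 is stricter: out-of-range values "will not be considered AEs unless they are associated with a clinical sign or symptom: IGF-1, IGF-1 SDS, IGFBP3, IGFBP3", whether or not the dose was titrated.

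On how data were recorded before Version 2.0, the rationale in the protocol's summary of changes says that "clinically significant laboratory values (including IGF-1 and IGFBP3) were categorically to be documented as AEs". It adds that investigators were obliged to give out-of-range IGF-1 and IGFBP-3 values that label, irrespective of clinical concern, if they wanted to titrate.

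SAP 8.1 then plans TEAE incidence by system organ class and preferred term over the whole extension, including tables by relationship to study drug. SAP 4.2 places the final analysis after the last subject's last visit. The subgroup list in SAP 9.4 contains neither protocol version nor calendar period.

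**The concern.** Safety is the primary objective, and incidence of AEs is the first safety endpoint listed in protocol 14.1.1 and SAP 3.3.1. The same asymptomatic IGF-1 value followed by the same titration could be an AE in one part of the trial and is not one in a later part. An incidence pooled over both parts has no single definition behind it, and its value depends on how much follow-up falls under each rule.

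The related-TEAE table is exposed as well as the overall one. The protocol describes IGF-1 and IGFBP-3 as pharmacodynamic markers of the drug, so an investigator could readily rate a high value as related. The filter that keeps mild, unrelated AEs off the case report form would then not remove it. Interim analyses, which SAP 4.1 allows at the sponsor's discretion, could carry a different mixture at each data cut.

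**Working it through.** The plan states no figure on this point, so there is none to reproduce. The check compares texts and adds one line of scale arithmetic.

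**1. Do the two current documents define the event alike?** No.

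| Finding | SAP 8.1 | Protocol 12.1.1 / 12.1.3 |
|---|---|---|
| Out-of-range laboratory value alone | Can be an AE | Condition for an AE not met |
| Same value with a diagnosis, sign or symptom, or needing treatment | Can be an AE | May be an AE |
| Out-of-range IGF-1 or IGFBP-3, no sign or symptom, dose titrated | Can be an AE | Not an AE |

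The difference is between two documents in force. It does not depend on the amendment log.

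**2. Was the recording rule in fact broader before Version 2.0?** The sponsor's rationale says so. The log is used here only as evidence of how data were recorded. The earlier rule covered clinically significant values, not every abnormal one. For IGF-1 and IGFBP-3, the need to apply the label before titrating widened it in practice.

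**3. Were data collected while the earlier rule applied?** Yes. The March 2019 US amendment, now folded into Version 2.0, justifies dropping repeat IGF-1 tests by reference to results already seen in the trial.

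**4. When did the rule change?** January 2020 is the date of the amendment. Protocol 15.9 requires ethics and regulatory approval before an amendment is implemented, so the change is staggered by site and country.

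**5. Does the SAP separate the two periods?** No. Sections 4.2, 5, 8.1 and 9.4 contain no split by protocol version or period and no sensitivity analysis for laboratory-only events.

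**6. Scale.** Let *N* be the number treated and *k* the number of children whose only TEAE is a laboratory finding that fails the Version 2.0 condition. Excluding those events lowers the any-TEAE incidence by 100 × *k* / *N* percentage points.

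- Protocol, *N* about 300: 1% is 0.01 × 300 = 3 children; 100 × 3 / 300 = 1 point.
- SAP 3.2, *N* about 400: 1% is 0.01 × 400 = 4 children; 100 × 4 / 400 = 1 point.

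The formula also serves the related-TEAE table, with *k* counting children whose only *related* TEAE is such a finding. The documents give *k* for neither table.

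**The case against.** The strongest reply is that SAP 8.1 does not create the mixture. Its verb is permissive, it has no rule that turns laboratory data into AEs, and SAP 8.4 sends values judged clinically significant to a separate listing. An event reaches the TEAE tables only if an investigator recorded it under the protocol. This stands. A reader might infer that the SAP counts every abnormal laboratory value as an AE, and the text does not support that. The mixture comes from the amendment, so rewording 8.1 alone would change no count.

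It can also be said that the problem is partly visible already. TEAEs are tabulated by preferred term, all AEs are listed, and onset dates are collected, so laboratory terms can be picked out. That helps with individual terms. It does not yield an overall or related TEAE incidence under one rule.

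Four further inferences are tempting and unsupported:

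- **A clean break in January 2020.** That is a document date; implementation followed local approval.
- **Bias in a known direction between parent-study groups.** No roll-over dates by group are given, the two CT-301 arms were randomised within one trial, and the planned summaries are descriptive.
- **A definite number of affected children.** The documents report no count of laboratory-only AEs and no division of follow-up between the two rules.
- **Double counting of high IGF-1.** The IGF-1 tables and the AE tables are separate outputs and are never summed.

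Finally, taking investigator-recorded events out of the main safety table after the fact, on sponsor review, would invite criticism. That objection is sound, and the fix respects it.

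**Conclusion.** The point holds in a limited form. SAP 8.1 carries a definition that the current protocol has dropped. The planned TEAE tables pool events recorded under a broader and then a narrower laboratory rule, and nothing in the SAP shows how far the result depends on that change.

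The size is unknown: 1 percentage point of any-TEAE incidence for each 1% of children whose sole TEAE is such a finding. This rests on two assumptions: that the sponsor's account of the earlier recording practice is accurate, and that sites followed it. The events most likely to be affected are IGF-1 and IGFBP-3 values labelled clinically significant to permit titration, since mild, unrelated AEs were already left off the form. The issue is one of consistency and interpretation, and it is cheap to resolve before lock.

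**What to change.** 1. Replace the AE definition in SAP 8.1 with that of protocol 12.1.1 and 12.1.3, and update the protocol version cited in SAP section 1.
2. Before database lock, have a medical reviewer flag each AE that consists only of an out-of-range laboratory value and would not meet the Version 2.0 condition. Write the flagging rule into the SAP beforehand.
3. Keep the as-recorded TEAE tables as the main tables. Add a sensitivity table of all TEAEs and of related TEAEs without the flagged events. An alternative is to split both by the protocol version in force at the site at AE onset, which needs implementation dates by site.

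The cost is a paragraph of SAP text, a short medical review of laboratory preferred terms and one extra set of tables. The sensitivity incidence can only equal or fall below the as-recorded one, so the two should be shown together. No IGF-1 information is lost, because values above 2.0 and 3.0 SDS have their own endpoint and table in SAP 8.3.

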The reason for administering the exact volume as per [Table 1](#) (rather than calculating the exact dose) is as follows. When the GH Auto-Injector, a unique device developed specifically for the administration of TransCon hGH, becomes available, subjects will be switched from the administration of TransCon hGH by syringe and needle to the GH Auto-Injector in the US only.

With the GH Auto-Injector, TransCon hGH will be provided in single-use DCCs as detailed in [Section 9.1.2](#). Multiple DCC presentations (dose strengths) will be available containing approximately 20% incremental increases in dose to support increasing weight ranges. Thus, each DCC will contain a specific quantity of TransCon hGH to support a specific weight range consistent with [Table 1](#), as shown in [Table 2](#).

Dosing based on fixed volumes or DCCs for weight ranges with 20% bracketing ensures that all subjects will receive an average of 0.24 mg hGH/kg/week over the course of the trial.

Table 2 TransCon hGH (ACP-011) Dosing Table for the GH Auto-Injector and DCC Product

Subject Weight (kg)	DCC Dose Strengths (mg hGH)
11.5 – 13.9	3.0
14.0 – 16.4	3.6
16.5 – 19.9	4.3
20.0 – 23.9	5.2
24.0 – 28.9	6.3
29.0 – 34.9	7.6
35.0 – 41.9	9.1
42.0 – 50.9	11.0
51.0 - 60.4	13.3
60.5 – 69.9	7.6 + 7.6
70.0-84.9	9.1 + 9.1
85.0– 100.0	11.0 + 11.0

hGH = human growth hormone; kg = kilogram; mg = milligram

After the GH Auto-Injector is available (in the US only), for subjects whose weight is below the ranges listed in [Table 2](#), TransCon hGH will continue to be administered using syringe and needle. Once the subject’s weight has reached a weight range listed in [Table 2](#), TransCon hGH will be administered using the GH Auto-Injector.

Please note that there are slight differences in the boundaries of the highest weight brackets in [Table 2](#) versus [Table 1](#). These differences are necessary to maintain the approximate weight-based dose of 0.24 mg hGH/kg/week, when administering two (duplicate) DCCs per week to achieve an absolute total TransCon hGH dose > 13.3. mg/week.

For those subjects who have historically been dose-titrated to a bracket different (higher or lower) than expected for weight, and have had interval weight gain into a higher bracket, the investigator has the option to either:

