- ³ Medications and health status: Interval history only to be recorded in case of new disease states since the last visit of the prior trial; disease states diagnosed since the initiation of the prior trial (eg, new onset migraines) are medical history; Medical history from the prior trial will be carried forward into this trial's database; Ongoing AEs from the prior trial will be followed until resolution or stabilization; Review of subject diary from the prior trial; Current therapies.
- ⁴ Vital sign measurements include heart rate, blood pressure, respiratory rate and body temperature, which should be performed after the subject has rested for at least 5 minutes.
- ⁵ Height should be measured at each visit at approximately the same time of day, preferably by the same auxologist.
- ⁶ Blood sample collection – A includes IGF-1, IGFBP-3, antibodies against hGH and PEG, and for females of child-bearing potential hCG. If warranted, TransCon hGH, hGH, and PEG serum levels may be analyzed for the interpretation of immunogenicity titers
- ⁷ Blood sample collection – B includes mPEG, hormone/glycemic status (TSH, FT4, FT3, morning cortisol, and HbA1c), chemistry, hematology, and lipid panel. Fasting not required.
- ⁸ Bone age x-ray may not be required at Visit 1 if there is documentation of a bone age x-ray performed within the past 52 weeks. However, if subject's prior documented bone age was > 12.0 years, and it was performed greater than 9 months prior to Visit 1, a bone age x-ray should be performed within approximately 4 weeks of Visit 1. Bone age x-ray may also be performed at any time, if clinically indicated.
- ⁹ Once the GH Auto-Injector is available, transition to the GH Auto-Injector will occur in the US (only) at the next regularly scheduled trial visit when thorough training on preparation and administration will occur.
- ¹⁰ At Visit 1, the C&OS-P, CSDS-P, and CSDS-C should be completed for all subjects.

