2.1. Primary Objective

- To assess long-term safety of weekly TransCon hGH in children with GHD previously treated in a phase 3 TransCon hGH trial

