The total duration of participation for each subject in the trial will therefore depend on the conditions listed above in the Treatment Period, and may be different in different countries and regions.

Figure 1: Overall Trial Design

Visit 1 = Final visit of prior trial	Visit 1	Week 6	Visit 2	Visit 3	Visit 4	Visit 5	Continues every 3 months
	Week 1 Initial Dose in this trial	Week 6 Before 6 th Dose PROs in Diary	Week 13 (± 2 Week)	Week 26 (± 2 Week)	Week 39 (± 2 Week)	Week 52 (± 2 Week)	
	All Visits are 5 Days Post-Dose (± 1 Day)						
	Treatment Period - dose adjustments every visit as needed						
Indefinite (visits every 3 months)							

Note Week 6 is not a clinical visit. For subjects who were treated with Genotropin in the TransCon hGH CT-301 trial, patient-reported outcome questionnaires within the subject diary will be completed immediately prior to the 6th study drug administration (Week 6).

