4.1. Interim Analysis

This is an open label study. Interim analysis can be done at sponsor's discretion to support regulatory submission or product planning. An independent safety monitoring committee (ISC) will be established to monitor subject safety. Data used for ISC meetings will be handled according to the ICH E9 guidelines and therefore will not affect the study design and conduct from an efficacy perspective.

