4.2. Final Analysis

All final, planned analyses identified in this SAP will be performed after the last subject has completed the last study visit and end of study assessments, and all relevant study data have been processed and integrated into the analysis database.

5. General Statistical Considerations

All analysis will be performed based on full analysis set and summaries will be presented overall and for subjects rolling over from Study CT-301 and Study CT-302 TransCon hGH group and Genotropin group separately. Descriptive summaries will be provided where appropriate for each of the primary and secondary variables.

Continuous, quantitative (absolute values at each time point and change from baseline if applicable) variable summaries will include the number of subjects (n) with non-missing values, mean, standard deviation (SD), standard error (SE), median, minimum, and maximum, unless otherwise specified.

Categorical, qualitative, variable summaries will include the frequency and percentage of subjects who are in the particular category. In general, the denominator for the percentage calculation will be based upon the total number of subjects in the study population for the cohorts, unless otherwise specified.

All data collected on eCRF will be presented in listings.

All analysis will be performed using SAS® Software version 9.4 or later.

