9.4. Subgroup Analysis

Efficacy variables including annualized HV, HSDS and IGF-1 SDS, demographic and baseline characteristics and TEAE may also be summarized based on the following subgroups.

- Age (< 3 years, ≥ 3 to <6 years. [≥ 6 to <11 years for girls, ≥ 6 to <12 years for boys] and [≥ 11 years for girls, ≥ 12 years for boys])
- Gender
- Asian vs Non-Asian
- Tanner Stage
- US vs. Non-US

For US sites, subjects will be switched from syringe to auto-injector during the study. The following analysis will be repeated for US subjects for auto-injection:

- Exposure/compliance
- TEAEs
- Local Tolerability
- Anti-body (only the positive vs negative)
- Device related PROs

10. Pharmacodynamics Analyses

The Pharmacodynamic (PD) endpoint, Serum IGF-1 SDS will be collected at 5 days \pm 1 day post-dose. Listings will be generated for PD endpoints.

11. Patient-Reported Outcomes

All Patient-Reported Outcomes used in this trial have been assessed for understanding by GHD patients and their parents/legal guardians/caregivers as intended by the Sponsor in a prior Cognitive Debriefing study per the Guidance for Industry. Questionnaire are administered during the study. The following endpoints are also collected:

- Preference for TransCon hGH or commercially available daily hGH treatment
- Satisfaction with daily hGH and weekly TransCon hGH over time

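### TEAEs are planned only as crude percentages of subjects despite open-ended follow-up, and no rule assigns events to the auto-injector period

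*SAP*

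**What the plan says.** The primary objective in SAP 2.1 is: "To assess long-term safety of weekly TransCon hGH in children with GHD previously treated in a phase 3 TransCon hGH trial". The TEAE output in SAP 8.1 is: "Summaries of incidence rates (frequencies and percentages) of individual TEAEs by MedDRA SOC and preferred term will be prepared". The parenthesis fixes what is meant by a rate, namely a count and a percentage of subjects, each counted once per preferred term. SAP section 5 sets the default, under which "the denominator for the percentage calculation will be based upon the total number of subjects in the study population for the cohorts", and SAP 8.1 names no other. Protocol 14.4 likewise plans counts and proportions.

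The TEAE window in SAP 8.1 runs from the first extension dose to the end of study, with no split by device.

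Follow-up has no fixed length. SAP 3.1 lets treatment run until approval, alternative access or the end of appropriate paediatric therapy, and says that participation "may be different in different countries and regions". Under Protocol 10.1 a child also completes when the epiphyses close. SAP 4.1 allows interim analyses at the sponsor's "discretion to support regulatory submission or product planning".

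On the device, SAP 9.4 says: "The following analysis will be repeated for US subjects for auto-injection". The list that follows includes exposure and TEAEs. Protocol 18.2, footnote 9, says that once the device is available, "transition to the GH Auto-Injector will occur in the US (only) at the next regularly scheduled trial visit". Protocol 9.3 adds that for children lighter than the Table 2 ranges, "TransCon hGH will continue to be administered using syringe and needle" until they reach those weights. SAP 8.6 tabulates total treatment duration, separately from TEAEs.

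**The concern.** For a fixed group, the percentage with at least one event rises with follow-up even when the underlying rate is constant. Here follow-up can differ by country, by age or pubertal stage (through epiphyseal closure), and between data cuts. SAP 9.4 names age, Tanner stage and US versus non-US as possible TEAE subgroups. Without time at risk, percentages from these strata, or from two cuts, cannot be compared.

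The auto-injector table has two problems. Time on the device is only part of each switching child's follow-up and starts at a different point for each child, but SAP 9.4 gives no matching time at risk. In addition, no rule says which events belong to the device period. With the single window in SAP 8.1, an event on syringe months before the switch can appear in the auto-injector table. Safety in auto-injector users is a secondary objective in Protocol 6.2, so this table will be relied on.

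**Working it through.** **Inputs.** The measure and window come from SAP 8.1, the denominator from SAP 5, open-ended follow-up from SAP 3.1 and Protocol 10.1, and switch timing from Protocol 9.3 and 18.2. The documents state no AE rate, follow-up length or time on device, so the plan has no figure to reproduce. All rates and durations below are assumptions: a constant rate r of 5, 10 or 30 per 100 patient-years, the same on syringe and device.

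**1. Crude percentage against follow-up.** p(t) = 1 − exp(−rt).

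| r per 100 patient-years | 0.5 y | 1 y | 1.5 y | 2 y | 3 y |
|---|---|---|---|---|---|
| 5 | 2.5% | 4.9% | 7.2% | 9.5% | 13.9% |
| 10 | 4.9% | 9.5% | 13.9% | 18.1% | 25.9% |
| 30 | 13.9% | 25.9% | 36.2% | 45.1% | 59.3% |

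With no change in risk, p(3)/p(1) is 2.86, 2.72 and 2.29.

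**2. Device against syringe, events correctly assigned to periods** (ratios from unrounded values).

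| r per 100 patient-years | 0.5 y device / 1.5 y syringe | 1.5 y device / 0.5 y syringe |
|---|---|---|
| 5 | 0.34 | 2.93 |
| 10 | 0.35 | 2.86 |
| 30 | 0.38 | 2.60 |

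The first-event rate is p(t) divided by the expected time to first event or end of period, which is p(t)/r. It equals r in both periods, a ratio of 1.0 in every row.

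**3. A real difference can be hidden.** A doubled rate of 20 per 100 patient-years over 0.5 year on device gives 1 − exp(−0.10) = 9.5%. That is below the 13.9% from 10 per 100 patient-years over 1.5 years on syringe.

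**4. Window taken literally.** If the auto-injector table counts everything since the first extension dose, a child with 1.5 years on syringe and 0.5 year on device contributes p(2) instead of p(0.5). That is 9.5 against 2.5%, 18.1 against 4.9%, and 45.1 against 13.9%, or 3.9, 3.7 and 3.2 times the device-period figure. With 0.5 year on syringe and 1.5 years on device, p(2)/p(1.5) is 1.3, 1.3 and 1.2.

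**5. What the tabulated duration recovers.** Subjects with an event over total treatment time understates the first-event rate by 1 − p(t)/(rt). At 1, 2 and 3 years the shortfall is 2.5, 4.8 and 7.1% at 5 per 100 patient-years; 4.8, 9.4 and 13.6% at 10; and 13.6, 24.8 and 34.1% at 30.

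**6. Why the clock should restart at the switch.** Suppose children differ in risk (assumed gamma frailty, mean 1, variance 1) and the device has no effect. With one year on each, a first-event clock from Day 1 gives device/syringe rate ratios of 0.95, 0.91 and 0.79; a restarted clock gives 1.00. With one year on syringe and 0.5 year on device, the restarted clock gives 1.01, 1.02 and 1.06, and all events over total exposure gives 1.00.

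**7. TEAE end date (minor).** If the last visit is 4 to 6 days after the last dose, 8 to 10 of the 14 post-dose days could fall outside the window. As a share of time at risk this is 8/(365.25y + 14) to 10/(365.25y + 14): 2.1 to 2.6% at y = 1 year and 0.7 to 0.9% at y = 3. It is zero if end of study already covers the 14 days.

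**The case against.** The SAP delivers what the protocol asks: the endpoint is incidence of AEs, and Protocol 14.4 specifies counts and proportions. The trial has no concurrent comparator, and neither document plans a between-group or device test. SAP 9.4 plans no syringe-period table. The planned analyses follow the last subject's last visit, and interim cuts are optional. Duration is tabulated and repeated for the auto-injector, and AEs and exposure are listed, so a rate could be derived later. For uncommon events the rough rate is close (2.5 to 7.1% low at 5 per 100 patient-years).

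All of that stands, and it makes this an improvement to a descriptive analysis. It does not remove the gap. Person-time to first event cannot be read from the planned tables, the shortfall grows for common events, and no listing replaces a missing rule for assigning events to a device period.

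A reader might infer that the plan will make the auto-injector look falsely safe. The documents do not support that: they give neither period length, and step 2 reverses when device time is the longer. A reader might also infer that the parent-study groups have unequal follow-up. This is not shown for the two CT-301 groups. For CT-302 the direction is unknown, because Protocol 5.3 has that trial admitting children from 6 months to 17 years of age.

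**Conclusion.** The point holds as a gap in the primary safety output. TEAE percentages over cohort size depend on length of follow-up, and neither document supplies time at risk for them. As written, SAP 8.1 and 9.4 let syringe-period events into the auto-injector table. The absence of a person-time rate and of an assignment rule is certain from the text. The size is illustrative only: ratios of 0.34 to 0.38 or 2.6 to 2.9 with no true difference, assuming constant equal rates of 5 to 30 per 100 patient-years and periods of 0.5 and 1.5 years. No stated figure is wrong and no planned test is affected.

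**What to change.** **(a) SAP 8.1.** Keep the crude percentages. For all, related, serious and discontinuation TEAEs, add subjects with a first event per 100 patient-years at risk, overall and by parent-study group. State three limits:

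- The groups enter with different prior TransCon exposure: none, about 6 months or about 52 weeks.
- The rate assumes a roughly constant hazard.
- The numerator is filtered. Mild unrelated AEs are not recorded except by site preference (Protocol 12.1.1), and injection-site reactions count only under the conditions in Protocol 11.11.1.

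**(b) SAP 9.4.** Count auto-injector TEAEs by onset on or after the first auto-injector dose, taken from the diary or dosing record rather than the dispensing date. Restart time at risk there, so that a child with an earlier syringe-period event still contributes device time. Show the syringe period of the same US subjects beside it, with all events over total period exposure for both. Label the contrast descriptive and confounded with time on therapy and age.

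**(c) Separate minor item.** When the SAP is updated from Protocol 1.0, define the TEAE end date in SAP 8.1 and 5.2 to match the AE collection window, and reconcile Protocol 8.2, 9.6.2 and the two statements in 12.1.3. The effect is at most about 0.7 to 2.6% of time at risk and may be none.

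**Cost.** SAP wording, programming and a short protocol clarification for (c). No new data collection is expected: AE onset dates (Protocol 12.1.3) and diary dose dates (Protocol 11.8) are already recorded. The Table 3 duration is not enough, because time to first event must be derived for each table row and period. The downsides are a rate that depends on its hazard assumption and an all-events count in which a worsened AE enters as a new event (Protocol 12.1.3).
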